### **7.1. Primary Efficacy Endpoint**

Time to culture negative status in liquid media over 8 weeks will be analysed using a Cox regression model, censoring for death and lost to follow up/withdrawal to estimate the hazard ratio. This model assumes proportional hazards. This means that the hazard rates for participant subgroups are proportional over time during participant follow-up. A program that tests the proportional hazards assumption in the Cox model (estat phtest for Stata) will be used. In the case where there is adequate evidence that the proportional hazard assumptions are violated at the 5% level (i.e.  $p<0.05$ ), then the restricted mean survival time method (RMST) will be used. Data will be described using Kaplan-Meier plots.

For the 8 week culture conversion endpoint the time will be taken from randomisation until the first occurrence of achieving culture negative status in liquid media over 8 weeks. For participants who do not achieve culture negative status, time will be taken from randomisation to 8 weeks (and censored). Participants who die or are lost to follow up/withdrawn will be considered as not achieving culture negative status unless they have achieved a culture negative status prior to death or being lost to follow up/withdrawn. The last known visit date will be taken for any participants who are missing the date of their 8-week visit. Participants negative at baseline (but eligible for the trial based on a positive result at screening) will not be included in this primary time-to-event analysis.

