## **4. Sample Size**

For the primary endpoint, time-to-negative culture conversion at 8 weeks, 150 participants per arm (DS-TB participants) will provide more than 99% power (5% two-sided significance) to detect a hazard ratio (HR) of at least 2 (for 4BPaMZ vs. HRZE), assuming 50% of control participants are culture negative by 8 weeks. If only 25% of the control arm remain culture positive at 8 weeks, then this sample size will still retain more than 93% power to detect a HR of least 2. Note, non-randomised MDR participants will not be formally compared to any randomised group.

For the key secondary efficacy endpoint of clinical outcome at 12 months from randomisation, 150 participants per arm will provide 74% power at the two-sided 5% significance level based on assumptions using data from the largest most recently completed phase 3 TB treatment trial which used the same control arm [2]. That is, assuming 16% of participants in the control arm are unfavourable and 13% are unassessable at 12 months post randomisation. A non-inferiority margin of 12% is chosen and justified below.

This trial aims to demonstrate that the experimental regimen administered for 4 months to participants with DS-TB is not inferior to the standard 6-month control regimen using a non-inferiority margin of 12%, chosen based on the following rationale. The best estimate for the treatment effect (also known as M1 in guidance documents for non-inferiority trials) of the current standard treatment (HRZE) is derived from modern clinical trials of this treatment compared to historical, natural history trials. Based on the above reference, an estimate of the favourable rate observed with standard HRZE therapy of 84% is used. The WHO estimates that the case fatality rate for untreated smear positive pulmonary tuberculosis is 70%, and this estimate was confirmed in a systematic review in 2011 [3]. Therefore, an estimate of 30% for the favourable rate of placebo may be contrasted with the 84% favourable rate of the standard HRZE therapy. Based on these data, the best available point estimate for M1 (the overall treatment effect of HRZE, expressed as a risk difference) is 54%. A selection of 12% for M2 (the non-inferiority margin) would represent less than 25% of the point estimate of M1, thus assuring that the lower bound of the NI margin preserves more than 75% of the estimated treatment effect of the HRZE regimen.

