## **7. Efficacy Statistical Analysis**

All efficacy outcomes will be analysed for superiority with the exception of the proportion of participants who have an unfavourable outcome at 12 months and at 24 months. These will be analysed for non-inferiority with a non-inferiority margin of 12%.

All superiority analyses for efficacy, apart from the interim analysis (see §7.3), will be two-sided and considered statistically significant at the 5% level.

All efficacy analyses will be adjusted for the stratification variables (HIV status and cavitation) unless otherwise stated and considered primary. Unadjusted analyses will also be considered for key endpoints.

Additional baseline covariates listed in §7.4 will be considered for a secondary adjusted analysis for key efficacy endpoints.

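### A proportional-hazards test that is not tied to the treatment term decides whether the primary 8-week result is a Cox hazard ratio or RMST

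*SAP*

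**What the plan says.** Section 7.1 of the SAP sets the primary method: "Time to culture negative status in liquid media over 8 weeks will be analysed using a Cox regression model". Participants who do not convert are censored at 8 weeks. It then adds a check: "A program that tests the proportional hazards assumption in the Cox model (estat phtest for Stata) will be used". The consequence follows: "In the case where there is adequate evidence that the proportional hazard assumptions are violated at the 5% level" (p<0.05), "then the restricted mean survival time method (RMST) will be used". RMST is therefore a replacement for the hazard ratio, not a sensitivity analysis; section 7.1.1 lists only multiple imputation under that heading.

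The model being tested is fixed by section 7: "All efficacy analyses will be adjusted for the stratification variables (HIV status and cavitation) unless otherwise stated and considered primary". It therefore has three terms: treatment, HIV status and cavitation. Section 7 also says that superiority analyses "will be two-sided and considered statistically significant at the 5% level".

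Section 7.1 leaves four things open:
- whether the whole-model or the treatment-specific result of the test decides;
- the time scale of the test;
- the RMST truncation time;
- whether RMST is adjusted for HIV status and cavitation.

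The SAP gives no operating characteristics for the two-step rule.

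**The concern.** One p-value chooses the effect measure of the primary endpoint, and the SAP does not link that p-value to the treatment effect. Section 7.1 describes proportional hazards as a property of the model and of participant subgroups, and names the program without restricting it to one term. Read that way, the null hypothesis is that all three terms are proportional. What matters for the treatment estimate is only whether the treatment effect is constant over the 8 weeks.

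Four consequences are possible:
1. A changing cavitation or HIV effect alone moves the primary result from a hazard ratio to an RMST difference.
2. A treatment effect that does change is usually not detected, so a non-significant test gives little support for a constant hazard ratio.
3. When the switch does fire, the trial may be diverted to a less sensitive test.
4. The RMST p-value is read against 5% although RMST is used only in data sets selected by the first test.

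The Cox test of no treatment effect does not need proportional hazards to be valid, so the superiority test needs no gatekeeper.

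**Working it through.** **Step 1. The SAP's own power figure.** Section 4 states that "150 participants per arm (DS-TB participants) will provide more than 99% power" for a hazard ratio of 2 with 50% control conversion, two-sided 5%.
- Experimental conversion: 1 - (1 - 0.5)^2 = 75%.
- Expected events: 150 × (0.50 + 0.75) = 187.5.
- Schoenfeld: z = sqrt(187.5 × 0.25) × ln 2 - 1.96 = 6.847 × 0.693 - 1.96 = 2.79, so power is 99.7%.

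The figure reproduces for Cox under proportional hazards. It does not cover the switch.

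**Step 2. Inputs for simulating the rule.**
- From the SAP: 150 per arm, 1:1 allocation (section 1.2), 50% control conversion and hazard ratio 2 (section 4), 8-week horizon and p<0.05 trigger (section 7.1), adjustment for HIV status and cavitation (section 7).
- Assumed: about 60% cavitation; 15-20% HIV positive; mostly weekly event times (section 7.3.1 mentions week 7 and week 8 results), with continuous times as an alternative; hazard ratios changing at week 4; constant or rising conversion hazard (Weibull shape 1 to 3); RMST to 8 weeks, unadjusted. Ranges below span different choices of these inputs.

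Only 150 per arm is used. Section 7.3.1 says that if the sample size is increased the 12-month outcome becomes primary, and section 7.3.4 gives 225 per arm as the new size.

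**Step 3. A covariate triggers the switch (treatment hazard ratio constant at 2).**

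| Covariate hazard ratio, weeks 1-4 then 5-8 | Whole-model test fires | Treatment-only test fires |
|---|---|---|
| Cavitation 0.4 then 1.0 | 42-51% | 3-5% |
| HIV 0.5 then 1.5 | 47% | about 4% |
| Cavitation 0.6 then 0.8 | about 6% | 3-5% |
| All effects proportional | about 3-5% | – |

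**Step 4. A changing treatment effect is missed.** For a treatment hazard ratio of 2.5 then 1.5, the whole-model test misses 85-89% of trials. A treatment-only test misses 74-82%. Large changes (3 then 1, or 1 then 3) are detected by the whole-model test in 46-69%.

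**Step 5. Power.** With a delayed effect (hazard ratio 1 then 3, constant baseline hazard), Cox has about 93% power and the two-step rule about 50%. With an early effect that fades (3 then 1.0), RMST has 99.6% and Cox 95%.

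**Step 6. Null behaviour with the whole-model trigger.** Selected scenarios, 60,000 trials each, roughly half of participants converting:

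| Scenario | Switch fires | RMST rejects, given a switch | Overall rejection |
|---|---|---|---|
| Continuous times, shape 1.5 | 5.0% | 10.9% | 5.4% |
| Weekly times, shape 1.5 | 3.6% | 11.8% | 4.2% |
| Weekly times, shape 3 | 3.2% | 17.4% | 3.9% |
| Weekly times, shape 2, cavitation 0.5 then 0.8 | 11.1% | 10.9% | 4.5% |
| Continuous times, shape 2, HIV 0.5 then 1.5 | 29.7% | 7.1% | 5.7% |

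Overall rejection = Cox rejection + P(switch) × (RMST rejection given a switch - Cox rejection given a switch). For the third row: 0.0344 + 0.0321 × (0.1742 - 0.0327) = 0.0389. Across all scenarios run, RMST rejection given a switch is about 6-19%, and overall rejection is 3.0-5.7%.

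In the last two rows, where a covariate is non-proportional, Cox alone rejects in 3.7% and 5.2%. Its null test is not harmed by that covariate.

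**The case against.** The strongest reply is that the program, threshold and fallback are all prespecified, Kaplan-Meier plots are shown in any case, and overall type I error is held. That is correct. A reader might infer from the conditional rejection rates that the rule inflates the trial's false-positive rate. It does not: with proportional effects the switch is rare under the null, and the overall rate stays at about 3-6%. Nor is there one fixed conditional rate. Figures of 16-19% need weekly times and a steeply rising conversion hazard. When strong covariate non-proportionality causes the switch, the rate falls to about 6-7%, so the first and fourth consequences are largely not additive.

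Second, the whole-model test is a reading. A reader might take it as stated, but section 7.1 names a program and does not say which of its results decides. If the sponsor meant the treatment-specific test, covariate triggering disappears. What stands is that the text allows both, and two analysts could then report different primary estimands from the same data.

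Third, the covariate figures depend on the assumed size of the change. The SAP gives no source for a cavitation hazard ratio of 0.4 then 1.0, and the mild case adds little to the base rate.

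Fourth, keeping the hazard ratio regardless means that it will sometimes be reported when it is not constant. That also stands, but the present rule mostly has the same result, because it misses moderate changes. Reporting RMST alongside in every case shows the reader both measures.

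**Conclusion.** The concern holds as a defect in how the primary estimand is chosen, not as a type I error problem. The natural reading of sections 7 and 7.1 lets HIV status or cavitation change the primary effect measure: in about 42-51% of trials under strong cavitation non-proportionality, and about 6% under mild. The test misses a moderate treatment change in about 85-89% of trials. With a delayed effect the rule can cut power from about 93% to about 50%. If RMST is reached by the switch, its p-value does not carry its nominal 5% meaning (about 6-19% under the null, conditional on a switch).

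All these sizes are for 150 per arm and rest on assumed cavitation and HIV prevalence, visit spacing, hazard shape and a change at week 4. The textual point, that the deciding test is not tied to treatment and that RMST replaces the hazard ratio, needs none of those assumptions. The change should be made; confidence in the exact sizes is moderate.

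**What to change.** In section 7.1:
- Make the Cox model adjusted for HIV status and cavitation, as section 7 already provides, the primary superiority test whatever the proportional-hazards test shows.
- Delete RMST as a conditional replacement.
- Always report the RMST difference to 8 weeks with its 95% confidence interval beside the hazard ratio, and state whether it is adjusted.
- Use the proportional-hazards test for the treatment term only, as a guide to interpreting the hazard ratio.

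The cost is SAP wording and one estimate already planned as the fallback; no new data or participants are needed. There is a small downside. Under clear non-proportionality the headline hazard ratio is an average over the 8 weeks, and with an early effect that fades Cox can lose a few points of power to RMST (95% against 99.6% for a hazard ratio of 3 then 1.0).

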#### **7.1.1. Sensitivity Analyses of Primary Efficacy Endpoint**

As a sensitivity analysis for the primary efficacy endpoint, multiple imputation [under the missing at random (MAR) assumption] will be used to account for missing culture results at missing visits, defined as missing when there are no culture results for any sample at a visit. Note: a contaminated result will be considered as such, up to and including week 8, after which it will be considered missing (for statistical analysis purposes). A seed of 102079 will be used, and 20 imputed values will be created for each missing observation in the multiple imputation model.

### **7.2. Secondary endpoints**

#### **7.2.1. Key Secondary Endpoint: Unfavourable Status at 12 months (Non-inferiority Comparison)**

For the proportion of participants who have an unfavourable outcome at 12 or 24 months, non-inferiority will be determined using the upper bound of the (two-sided) 95% confidence interval of the difference, relative to the 12% margin. If the upper bound of the two-sided 95% confidence limit for the difference (proportion with unfavourable outcome in the intervention arm less the proportion with unfavourable outcome in the control arm) is less than 12% (the margin of non-inferiority), the intervention will be considered to be non-inferior to the control arm on that comparison.

The difference in proportions of an unfavourable status at 12 months will be analysed using the Cochran-Mantel-Haenszel test.

##### **7.2.1.1. Secondary Bayesian analysis of Unfavourable Status at 12 months**

A Bayesian analysis of the key secondary endpoint will also be performed (as a secondary analysis) with the posterior distribution of the effect size graphed under different prior distributions (for example, sceptical, uninformative and optimistic). This analysis has advantages over a more standard frequentist analysis as direct probability statements can be made about the effect size and in addition, prior information about the size of the effect can be formally incorporated into the posterior estimation. While the uninformative prior will yield similar results as a standard frequentist analysis (i.e. with a point estimate and confidence interval), the Bayesian analysis provides a more intuitive interpretation about the effect of the intervention compared to control.

##### **7.2.1.2. Sensitivity Analyses for Unfavourable Status at 12 months**

The following sensitivity analyses on the key secondary endpoint are planned:

1. An analysis of participants in the TB-mITT and PP populations where reinfections are re-classified as unfavourable outcomes.
2. An analysis of the TB-mITT and PP populations treating all deaths as unfavourable.

#### **7.2.2. Unfavourable Status at 24 months**

Unfavourable status at 24 months will be analysed as described in the first two paragraphs of §7.2.1 for unfavourable status at 12 months.

#### **7.2.3. Time to Unfavourable Status**

Time to an unfavourable outcome will be analysed using a Cox proportional-hazards regression analysis. These analyses will be performed according to the mITT, TB-mITT and PP classifications. Time to event will be calculated in days from the date of enrolment up to the first date associated with the reason for unfavourable status or (if favourable) the date of the 12 months post randomisation visit or date last seen if they did not reach 12 month follow-up. Kaplan Meier plots will also be presented.

#### **7.2.4. Time to Sputum Culture Conversion to Negative Status**

For the mITT analysis population, time to culture negative status (first of two negative cultures without an intervening positive culture) will be analysed using survival analysis techniques, Kaplan Meier plots and Cox proportional hazard regression.

#### **7.2.5. Culture Conversion Status at 4, 6, 12 and 17 Weeks**

For the mITT analysis population, participants will be classified as being culture positive, culture negative, dead or unassessable at 4, 6, 12 and 17 weeks.

#### **7.2.6. Adherence**

The proportion of participants who have an adequate amount of treatment (see §3.3) will be tabulated. No formal comparisons will be performed.

#### **7.2.7. Weight and BMI**

Baseline weight and BMI and their change from baseline weight at week 8 and end of treatment and at 12 and 24 months after the end of therapy will be summarised by mean, median, IQR and range.

#### **7.2.8. TB Symptoms**

Each TB symptom will be summarised by n (%): none (0), mild (1), moderate (2), severe (3) at each visit collected as per the protocol: baseline, week 8, end of treatment, 12 and 24 months after the end of therapy.

In addition, baseline and change from baseline score at each time point listed above for each symptom and for total symptom score will be summarised by mean, median, IQR and range.

#### **7.2.9. Participant Reported Health Status**

Participant reported health status is measured by the 5 domains of EQ5D. These will be summarised at baseline, week 8, end of treatment and 12 month follow-up by randomised group. Change from baseline will be summarized at each follow-up assessment by mean, median, IQR and range.

#### **7.2.10. Predictors of Favourable Status at 12 and 24 months**

As an exploratory analysis, predictors of having a favourable outcome at 12 months and at 24 months will be investigated. Potential predictors will include, but are not limited to, baseline variables (see §7.4), culture negative status at weeks 4, 6, 8, 12 and 17 as well as time to culture negativity (as a continuous variable).

### **7.3. Interim Analyses**

#### **7.3.1. Overview**

There is one planned interim analysis for efficacy data. The interim analysis is based on an intermediate outcome of time to negative culture conversion status observed by 8 weeks. Following a review of these interim findings, consideration will be given to increase the sample size (pending funding availability) to adequately power the study on the key secondary 12-month clinical outcome. This would then become the primary efficacy endpoint. This adaptation is based on the Multi-arm Multi-stage (MAMS) framework [4-6].

The interim analysis endpoint (I) is time to negative culture conversion status observed by 8 weeks in the mITT population. The final analysis endpoint (D) is favourable status at 12 months. Therefore, as the interim endpoint is not the same as the final analysis endpoint this is denoted as  $I \neq D$  i.e. interim endpoint does not equal the final endpoint.

For the interim analysis, a single culture result at week 8, with no available future culture data, is sufficient to classify culture negative status at that visit (see §3.1.3). If all culture results are contaminated at week 8 and no future culture data is available, then the week 7 result is sufficient to determine status at week 8.

#### **7.3.2. Operating characteristics**

The power at each stage has been maintained at a high level ( $> 0.9$ ) to ensure an effective intervention has a high chance of proceeding beyond I (to minimise the chance of missing a result and not extending recruitment).

A 10% significance level ( $p=0.1$  one-sided) has been chosen for the first stage to allow in an event that the intervention seems to be performing poorly then the sample size will not be increased but stay as planned. At the first stage there is less concern about extending recruitment if the observed interim result is false so a higher than the conventional 5% (2-sided) level is chosen. But, the corresponding power has been chosen as 95% so that there is a high chance of proceeding to the 2nd (and final stage) if there is an indication of a treatment effect on the intermediate outcome measure.

Positive Predictive Value of the Control (PPVC) and of the Intervention (PPVE) were assumed 95%. Other values of PPVC were also considered to explore the sensitivity of the design on this assumed value. This is from a review of the literature and analyses on previously published TB trials [7].

Table 2 outlines the operating characteristics for both I and D.

Table 2. Operating characteristics for interim and final analysis		
	Interim (Phase 2)	Final (Phase 3)
Primary Outcome	Culture negative status	Favourable rate
Follow-up length	8 weeks	12 months
Significance level (1 sided)	10%	2.5%
Power	95%	90%
Control arm event rate	50%	84%
Treatment effect under (H0)	0%	-12% (NI margin)
Treatment effect under (H1)	25%	0%
Allocation ratio (E:C)	1:1	1:1
Attrition rate (LT FU rate)	0%	13%

### 7.3.3. Sample size calculation

The calculation was conducted in STATA using the NSTAGEBIN command ([Appendix §13.4](#)).

Currently, no software allows for selection of a HR at the interim stage and risk difference at the final stage. As such, the treatment effect in I was transformed from a HR to a risk difference for the sample size calculation. Assuming a control event rate of 50%, a HR of 2 was equivalent to an absolute risk difference of 25%.

### 7.3.4. Decision

The interim analysis will occur after approximately 60 participants randomised to the control arm have reached the 8-week primary endpoint. At the interim stage, a test on the risk difference between the two treatment arms on the I-outcome measure is carried out. The design and decision rule for the first stage was made based on target effect size of 2 on the hazard ratio scale. If the p-value of the test on the I-outcome is less than 0.1, accrual to both arms may continue to the final stage when a test on the D-outcome measure is carried out. Successfully moving to the final stage will mean increasing recruitment to 225 per arm i.e. to a total of 450 DS-TB participants and up to 225 DR-TB participants (if desired). This will adequately power the trial on the new primary endpoint in D with an overall power (both stages combined) of 86%.

### 7.4. Subgroup Analyses

As exploratory analyses to assess consistency of outcome, the following sub-group analyses (with tests for interaction) of the primary endpoint on the mITT analysis populations will be considered according to:

- HIV status
- Cavitation (images are to be reviewed in order for these data to be considered reliable)

- Age
- Sex
- Race
- Region
- Smoking status
- Alcohol intake
- Pyrazinamide resistance (pending numbers)
- Bedaquiline resistance (pending numbers)
- Time to positivity

